## ABSTRACT

The aim of this investigation is to characterize the restoration of posterior teeth using a novel, ultra-rapid polymerizing composite tooth restoration material by its comparison to restoration of posterior teeth using a conventional polymerizing composite tooth restoration material.

This prospective comparative clinical investigation uses a 'split mouth', within-subject design to evaluate an ultra-rapid polymerizing composite tooth restoration material for restoration of posterior tooth cavities and defects. Each participant will receive one conventional polymerizing (20-40 second) composite tooth restoration and one ultra-rapid polymerizing composite tooth restoration in different quadrants of their mouth (**Figure 1**). The primary outcome measure will be post-operative, self-reported tooth sensitivity. The polymerization light source is of high intensity; heat produced is limited by the 3-second exposure. While in vitro studies suggest little rest, heat-related sensitivity may be observed. Further, polymerization contraction can deform the vital tooth, causing fluid flow in the cells restricted in the tooth mineral that stimulates pain perception. Secondary outcome measures include a battery of measures that report on the integrity of the restorations over the 2-year evaluation period.

**Rationale:** Resin composite polymeric restorations have many major advantages for posterior tooth restoration including the ability to provide a more esthetic restoration, a lack of mercury, and the conservation of more of the remaining tooth. A major disadvantage is their technique sensitivity related to the assurance that the light-activated polymerization is complete. Large (posterior) restorations must be created incrementally, requiring significant time and effort. Alternative composites, so-called Bulk Fill composites, can be placed in large increments, but require extended polymerization times and may risk incomplete polymerization leading to failure. Polymerization is affected by the composite type, color, translucency and distance from the polymerization light source. The ability to cure composite increments in thicker increments and shorter time periods would allow for a more efficient and less time-consuming restoration insertion procedure. An ultra-rapid polymerizing composite offers clinical advantages. One consideration, however, is how the temperature and rate of polymerization influences the tooth response to heat and polymerization contraction. Transient temperature rises may elicit sensitivity and rapid changes in micron-scale tooth dimension may cause tooth sensitivity or pain.

## BACKGROUND

**Research problem and rationale:** Placing direct (in the oral cavity of the patient) composite fillings is one of most frequently performed interventions of a dentist in a dental office. Given the many intermediate steps, which have to be carried out under dry conditions in the wet mouth environment, this type of intervention is technique dependent. Many steps are time dependent due to polymerization of the composite resins and required bonding agents. The simplification and the increased efficiency of the procedure is, therefore, desirable from the point of view of the user and the patient and may influence positively the restoration quality through improved compliance (time). The objective of the ultra-rapid polymerizing composite (F-Composite 2 system) is to reduce this period of time. Hence, the individual layers of the filling, which may be up to 4 mm thick, and the adhesive (bonding agent) can be polymerized in 3 seconds. At present, curing times of up to 40 seconds are common. Composite polymers undergo polymerization contraction. Micron-level contraction of the restored tooth and causes fluid flow in the cells restricted in the tooth mineral which stimulates pain perception. The primary outcome measure of this study is self-reported post-operative tooth sensitivity or pain. The polymerization-related quality of the restoration will be evaluated over 2 years using clinical parameters and intraoral photographs.

**Experience / history relevant to the research.** To assure restorative integrity and quality, light-curing composite restoratives are usually applied in layers less than 2 mm in thickness. This increment technique, with each layer being separately cured assured complete polymerization. Few restorative composites currently on the market permit a higher layer thickness and the experiences from clinical studies are sparse. Even though some materials allow increment thicknesses of 4 mm, longer curing times are required and these are influenced by clinical factors such as compliance to time, polymer color, distance of curing light to polymer, and the curing light power. Generally, it has been impossible to cure 4 mm composites in less than 10 seconds. The main reason is that the upper limit of the available polymerizing light intensities is approximately 2,000 mW/cm^2.

Here, we will evaluate an ultra-rapid polymerizing composite system (F-Composite 2 system) composed of three components: F-Composite 2, Tetric EvoFlow Bulk Fill composites and the bonding agent, Adhese Universal. All are polymerized with a new type of curing light (Bluephase PowerCure) that emits blue light with a 1.5 times higher intensity than the currently strongest curing lights. The Bluephase PowerCure curing light emits an intensity of 3050 mW/cm^2. In conjunction with F-Composite 2, Bluephase PowerCure enables curing of the filling material to 4 mm thickness in only 3 seconds.

As the laboratory tests and technical data of F-Composite 2 have shown promising results, clinical results are now being gathered. As stated above, the focus here is the assessment of the frequency of postoperative sensitivity and the examination of the restoration quality over 2 years.

## OBJECTIVES

**Objective:** The objective of this 2 year split mouth comparative study is to determine whether the simplified placement procedure of a ultra-rapid polymerizing "F-Composite 2" System in single increments of up to 4mm with a reduced light polymerization time (3 seconds) yields the same clinical results as a widely used commercially available dental composite (Tetric EvoCeram Bulk Fill, Tetric EvoFlow Bulk Fill) requiring up to 40 seconds of light polymerization time.

**Hypothesis:** The rapid polymerization of a bulk fill composite system provides clinical posterior tooth restoration equivalent to conventional polymerization composite systems.

**Primary outcome measure:** post-operative tooth sensitivity.

**Secondary outcome measures:** restoration quality evaluation.

**Study duration:** 2 years.

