## STATISTICAL CONSIDERATION

The categorized clinical assessment (data see above) will be summarized by computing percentages for each category and used to describe any trends noted in the performance of the groups. In the analysis of categorical data of surface luster, surface staining, color match, material fracture, occlusal wear, tooth integrity, caries, marginal adaptation, marginal staining, contact point, post-operative hypersensitivity, patient's satisfaction, and radiographic examination, the frequency distribution over various categories will be calculated and reported. The published reports of post-operative sensitivity (primary outcome measure) range from 0 - 20% using the (Costa TRF 2017). However, "there is inconsistent, low-quality evidence regarding the difference in postoperative hypersensitivity subsequent to placing a dental cavity liner under Class I and Class II posterior resin-based composite restorations in permanent posterior teeth in adults."(Schenkel AB et al, Cochrane Database Syst Rev. 2016 Oct 25;10:CD010526) Selecting an informed 4% response of sensitivity with a 5% error at a 90% confidence interval, we would require 50 individuals to identify a significant response of sensitivity. Notably, a sample size of 50 subjects is not based on a statistical plan, but rather on guidelines put forth by the American Dental Association. Additionally, a Kaplan-Meier survival analysis will be performed to estimate the lifetime of the material based on clinical failures

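### The hypothesis is equivalence, but the primary outcome is only tabulated: with no margin, paired difference or interval, the planned analysis cannot support it

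*Combined protocol and SAP*

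**What the plan says.** The Objectives section asks whether the rapid system "yields the same clinical results as a widely used commercially available dental composite" and hypothesises: "The rapid polymerization of a bulk fill composite system provides clinical posterior tooth restoration equivalent to conventional polymerization composite systems". It names post-operative tooth sensitivity as the primary outcome. Background repeats this: "The primary outcome measure of this study is self-reported post-operative tooth sensitivity or pain". The Abstract and Study Design sections describe a split-mouth design in which each participant receives one restoration of each material.

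Statistical Consideration is the only statistical section. It says the categorised assessments "will be summarized by computing percentages for each category and used to describe any trends noted in the performance of the groups". For a list of outcomes that includes post-operative hypersensitivity, "the frequency distribution over various categories will be calculated and reported". The sample-size passage reads "Selecting an informed 4% response of sensitivity with a 5% error at a 90% confidence interval" and arrives at 50 individuals. It then adds that "a sample size of 50 subjects is not based on a statistical plan" and refers to professional-body guidelines instead. The one further analysis is a Kaplan-Meier estimate based on clinical failures.

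**The concern.** A claim of equivalence needs three things: a limit on how different the materials may be, an estimate of the difference, and a statement of its uncertainty to set against that limit. The plan supplies none of them for its primary outcome. Two columns of percentages can reveal a gross imbalance, but the absence of an obvious imbalance is not evidence of equivalence.

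The design also makes each patient their own control, yet no within-patient cross-tabulation is mentioned. The two marginal percentages do not show how many patients reacted on one side only, and that number determines the precision of the comparison.

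If the plan is followed exactly, any equivalence conclusion will rest on percentages that look alike, or on a margin chosen after the results are known. Neither would be credible.

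**Working it through.** **1. The plan's own figure.** Inputs from Statistical Consideration: rate p = 0.04, error d = 0.05, 90% confidence (z = 1.645, z² = 2.7055), 50 individuals. No formula is given.

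- Wald: n = z²p(1−p)/d² = 2.7055 × 0.0384 / 0.0025 = 41.6, so 42. At n = 50 the half-width is 1.645 × √(0.0384/50) = 4.6 points.
- Wilson: half-width = z√[p(1−p)/n + z²/(4n²)] / (1 + z²/n). At n = 50 this is 1.645 × √(0.000768 + 0.000271) / 1.0541 = 5.03 points; n = 51 brings it to 5 points or less.

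So 50 is close to what the precision of a single 4% rate requires. Only one rate is stated, and no version tried involves a difference between materials.

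**2. What 50 pairs say about the difference.** Let b and c be the numbers of patients sensitive on one side only, in each direction. The Tango paired score limits for the risk difference δ solve

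(b − c − nδ) / √{n[2q + δ(1−δ)]} = ±1.645,

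where q = [√(B² − 4AC) − B]/(2A), A = 2n, B = −b − c + (2n − b + c)δ, C = −cδ(1−δ).

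- b = c = 0: q = 0, and the equation reduces to δ = z²/(n + z²) = 2.7055/52.7055 = 0.0513.
- b = c = 2, trying δ = 0.0808: B = 4.08 and C = −0.1485, so q = (8.721 − 4.08)/200 = 0.0232. The statistic is −4.04/√[50(0.0464 + 0.0743)] = −1.645, so 0.0808 is the limit.

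| Discordant pairs each way | 0 | 1 | 2 | 3 | 5 | 8 | 10 |
|---|---|---|---|---|---|---|---|
| Half-width (points) | 5.1 | 6.8 | 8.1 | 9.2 | 11.1 | 13.5 | 14.9 |

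A 2/50 versus 2/50 table allows 0 to 2 discordant pairs each way, hence ±5.1 to ±8.1. A 10/50 versus 10/50 table (20%, the top of the published range the plan cites) allows 0 to 10, hence ±5.1 to ±14.9. A gross imbalance would show: 10/50 versus 0/50 gives 12.3 to 30.7 points.

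**3. Chance of showing equivalence with 50 pairs.** The documents give neither a margin nor a within-mouth correlation ρ, so both are assumed here. With equal true rates p, each discordant cell has probability p(1−p)(1−ρ). Power is the trinomial probability, summed over all (b, c), that the 90% score interval lies inside the margin.

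| True rate | Margin | ρ = 0 | 0.25 | 0.5 | 0.75 |
|---|---|---|---|---|---|
| 4% | ±5 | 0% | 0% | 0% | 0% |
| 4% | ±8 | 9.6% | 16.9% | 27.9% | 46.8% |
| 4% | ±10 | 43.5% | 57.5% | 72.7% | 88.6% |
| 4% | ±15 | 85.8% | 92.5% | 97.5% | 99.7% |
| 10% | ±10 | 4.7% | 14.4% | 35.0% | 67.4% |
| 10% | ±15 | 50.0% | 65.0% | 81.0% | 96.1% |
| 20% | ±10 | 0.0% | 0.7% | 7.9% | 41.3% |
| 20% | ±15 | 15.7% | 32.5% | 56.5% | 84.6% |

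The zeros at ±5 arise because the half-width is 5.13 points even with no discordant pair. A cruder normal approximation is more favourable: at 4% and ρ from 0 to 0.5 it gives 0% to 13% at ±5 and 64% to 95% at ±10. By either method, whether 50 pairs suffice depends on a margin the plan does not state.

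**The case against.** **The study may be meant as descriptive.** The Abstract's aim is to characterise the new material by comparison, Background says "the focus here is the assessment of the frequency of postoperative sensitivity", and the statistical section speaks of trends. On this view the word equivalent is loose usage. That reading suits those passages but not the Objectives section, which sets out to determine whether results are the same and states equivalence as its only hypothesis. A descriptive comparison in a split-mouth design would still need the paired difference and its interval.

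**The 5% error could be something other than one-rate precision.** No formula is given, Wald gives 42, and the sentence ends by speaking of identifying a significant sensitivity response, which suggests detection. So the one-rate reading is an inference, though the natural one. No test is attached to that phrase, and nothing there limits a difference between materials.

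**A within-patient table is not excluded.** True: the section is silent on pairing. The pairing is not stated to be used.

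**The hypothesis is wider than sensitivity.** It covers clinical restoration generally, and Kaplan-Meier addresses failures. This stands as a limit: meeting a sensitivity margin would not by itself establish equivalent restorations. Kaplan-Meier does not fill the gap for the primary outcome, and no between-material comparison is stated for it.

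**Sensitivity is recorded on a 0–10 scale, so a binary endpoint is a choice.** Also fair. The figures above use a binary endpoint because the plan's 4% and 0–20% are rates; a paired analysis of scores would have different precision. The omission itself is textual and does not depend on these figures.

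**Conclusion.** The concern holds and should be resolved before outcome data are analysed, because it affects the primary outcome and the only stated hypothesis. The planned tables could expose a large difference but cannot support equivalence.

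Identical observed rates leave a 90% uncertainty of ±5.1 to ±8.1 points at 4% and ±5.1 to ±14.9 points at 20%, depending only on the pairing. These half-widths assume a binary endpoint and 50 complete pairs at the analysed visit; lost pairs would widen them. The power figures also rest on assumed margins and correlations and on equal true rates. Under those assumptions and a 4% rate, ±15 is well powered throughout, ±10 only if the correlation is high, and ±5 is out of reach by the score interval. At a 20% rate even ±15 has only 16% to 85% power.

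**What to change.** Before outcome data are analysed, amend the protocol as follows.

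1. Name one sensitivity measure, one cut-off and one visit as the primary endpoint. If the assessment categories the statistical section points back to already define sensitivity, cite that definition.
2. Make the primary analysis the within-patient risk difference, F-Composite 2 minus conventional, with a paired 90% score interval. Report the 2x2 within-patient table beside it.
3. Choose one of two claims. Either prespecify and justify a margin and claim equivalence in sensitivity only if the interval lies wholly inside it, or reword the hypothesis as descriptive estimation of the paired difference.
4. Keep the 50 subjects and state the precision they offer as a range over possible discordance, using the half-widths above and noting that complete pairs are assumed.

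The cost is one amendment and minor programming. The paired data are already to be collected, so no visits or subjects are added. The real price falls on the sponsor, who must either commit to a margin that 50 pairs may be unable to meet or accept a weaker, descriptive claim.

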## ELIGIBILITY

**Subject population and source:** Subjects for this investigation will be recruited from patients seeking care within the clinics of the Dental School at the University of Illinois at Chicago. Fifty subjects ranging in age from 18 to 80 years of age will be recruited for this study.

The study PI and investigators will determine the eligibility of potential study participants.

**Eligibility** will be recorded in the recruitment log and will be maintained by the study coordinator. The recruitment log will be stored as part of the study documentation in a locked file cabinet in the locked office of the study coordinator. An eligibility checklist is attached.

## INCLUSION CRITERIA

Each subject must need at least 2 restorations in a vital posterior tooth.

Restorations may be indicated for caries removal and restoration, replacement of defective restorations (i.e. fractured, stained, unaesthetic), or requested replacement of unaesthetic restorations.

Must have given written consent to participate in the trial

Must be available for the required two year follow-up visits

Restored teeth must have occlusal contact with opposing teeth or restored teeth

Restoration width should be equal to or greater than 1/3 the distance from buccal to lingual cusp tips  
75% of the restorations Class II (minimum) and 25% Class I  
One, two or three surfaces per restoration  
Each Class II will have at least one proximal contact  
75% in molars (minimum) and 25% in premolars  
All restored teeth must have at least one occlusal contact in habitual closure  
Must have 20 or more teeth with evidence of bilateral posterior tooth contacts  
Teeth that require one or no cuspal build-ups  
Vital tooth  
Preoperative Sensibility on the teeth to be treated at maximum 3 on visual analog scale (10 = maximum).  
Patient wishes to be treated in this clinical trial after oral information by the operator and after signing the informed patient form.

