#### **EXCLUSION CRITERIA**

Allergy against ingredients of the materials under investigations (monomers)  
Do not meet all inclusion criteria above  
Have medical complications (organ transplants, long term antibiotic or steroid treatment, cancer or immunocompromised) or disabilities rendering them unable to tolerate the time required to complete the restorations or to provide adequate oral hygiene  
Suffer from xerostomia either by taking medications known to produce xerostomia or those with radiation induced or Sjögren's syndrome subjects.  
Have teeth with advanced or severe periodontitis or rampant caries or poor oral hygiene which may require extraction of the teeth to be restored  
Present with any systemic or local disorders that contraindicate the dental procedures included in this study  
Patients reporting having severe bruxing or clenching or need of TMJ related therapy  
Have tooth with exposed pulp during preparation or caries removal or require indirect pulp capping.  
Inclusion of teeth that are non-vital or that exhibit signs of pulpal pathology (pulpitis)  
If the working field cannot be maintained in a dry state for treatment.

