### Evaluation

Each restoration will be evaluated directly and indirectly (photographs) at baseline (one week after restoration placement), 6 months, 1 year, and 2 years.

Post-operative hypersensitivity of the teeth will be evaluated in the following way. The subject is asked to rate on a visual analogue scale VAS (0-10) whether the restored tooth suffers from pain due to cold, heat, sweet, biting or clenching. Additionally, the restored tooth will be tested with a stream of cold air (air syringe) and the subject is asked to bite on a cotton roll. For both tests the subject is asked to rate on a visual analogue scale VAS (0-10) whether the restored tooth suffers from pain. Additional elicitation of sensitivity will be achieved by cold stimulus (cold refrigerant spray) and VAS assessment.

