**APPENDIX 1**  
**SCHEDULE OF EVENTS**

Procedure	Screening	Preparation	Baseline	6 month	1 year	2 year
Preoperative radiograph	X					
Subject assignment #	X					
Preoperative sensitivity	X					
Preoperative photograph	x	X				
Photograph of cavity preparation		X				
Treatment		X				
Photograph	x	x	X	X	X	X
Direct Assessment						
Surface Luster			X	X	X	X
Surface Staining			X	X	X	X
Color Match			X	X	X	X
Material Fracture			X	X	X	X
Occlusal Wear			X	X	X	X
Tooth Integrity			X	X	X	X
Caries			X	X	X	X
Marginal Adaptation			X	X	X	X
Marginal Staining			X	X	X	X
Contact Point			X	X	X	X
Sensitivity			X	X	X	X
Patients View			X	X	X	X
Post-op Sensitivity			X	X	X	X
Radiographic examination	X					X
Indirect Assessment						
BW Radiograph	X					X
PA Radiograph (if necessary)			(X)	(X)	(X)	(X)
Complaints			X	X	X	X
Adverse events			X	X	X	X
Unanticipated Advers Effects			X	X	X	X

Ivoclar Vivadent, Inc.

By

[name]  
Manager of Scientific Services

Date

10/16/18

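### The pre-operative sensitivity score is used only for eligibility, so the primary outcome cannot separate new sensitivity from sensitivity present before treatment

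*Combined protocol and SAP*

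**What the plan says.** - **Eligibility.** The Inclusion Criteria set a ceiling: "Preoperative Sensibility on the teeth to be treated at maximum 3 on visual analog scale (10 = maximum". Teeth scoring 0 also qualify. The Exclusion Criteria add a limit: "Inclusion of teeth that are non-vital or that exhibit signs of pulpal pathology (pulpitis".
- **Collection.** The Schedule of Events has a row "Preoperative sensitivity", marked at screening only. It does not name the stimuli used.
- **Outcome.** The Objectives section makes "post-operative tooth sensitivity" the primary outcome. The Evaluation section has the patient rate the restored tooth on a 0-10 VAS for everyday triggers, then for an air stream and for biting on a cotton roll, and continues: "Additional elicitation of sensitivity will be achieved by cold stimulus (cold refrigerant spray) and VAS assessment". None of these ratings is related to the score taken before treatment.
- **Timing.** "Each restoration will be evaluated directly and indirectly (photographs) at baseline (one week after restoration placement), 6 months, 1 year, and 2 years". The visit called baseline therefore comes a week after curing.
- **Analysis.** Statistical Consideration lists hypersensitivity among the categorical items, for which "the frequency distribution over various categories will be calculated and reported". It describes no change from the pre-operative score, no adjustment for it, no VAS cut-off and no comparison of sensitivity between materials.
- **Hypothesis.** The rapid system is expected to be equivalent to the conventional one. No margin is stated.

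**The concern.** The Abstract and Background ask a causal question: do the heat and contraction of rapid curing provoke sensitivity? A post-operative level alone mixes what curing caused with what the tooth brought to the chair. A tooth rated 3 before and 3 after gets the same table entry as a tooth rated 0 before and 3 after.

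The cold spray sharpens the problem. It is applied to teeth that must be vital, so part of the response may be ordinary, and no pre-operative reading on that stimulus is specified for comparison.

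Two things are at stake. A background common to both groups can make the materials look more alike, under a hypothesis that they are alike. A difference in prior sensitivity between a patient's two teeth can be read as a material effect. The split-mouth design controls for the patient, not for each tooth's own history.

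**Working it through.** **1. Role of the score.** Read in order, the sections show one use of the pre-operative score (the entry cap), one collection point (screening), and no mention of it in the outcome description or the analysis.

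**2. The plan's own figure.** Statistical Consideration gives 50 patients beside a 4% rate, 5% error and 90% confidence. The usual precision formula gives n = z²p(1 − p)/e² = 1.645² × 0.04 × 0.96 / 0.05² = 41.6, so 42. At 50 the half-width is 1.645 × √(0.04 × 0.96/50) = 4.6 points, within the stated 5. The plan says that 50 comes from a guideline, so the gap between 42 and 50 is not held against it, and nothing below depends on it. The 4% is used as an input.

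**3. Yes/no outcome, equal carry-over.** Let p be the new-onset rate and q the share of teeth whose earlier sensitivity persists and meets the event definition.

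Observed rate = 1 − (1 − q)(1 − p). The difference between groups is (1 − q)(p_rapid − p_control).

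Inputs: p_control = 4% (the plan's figure, read as new onset), p_rapid = 8% (assumed), q = 0 to 20% (assumed), 50 teeth per material. SE = √{[r₁(1 − r₁) + r₂(1 − r₂)]/50}, where r₁ and r₂ are the observed rates and teeth are taken as independent.

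| q | Control | Rapid | Difference (points) | Ratio | Difference/SE |
|---|---|---|---|---|---|
| 0 | 4.0% | 8.0% | 4.0 | 2.0 | 0.85 |
| 10% | 13.6% | 17.2% | 3.6 | 1.26 | 0.50 |
| 20% | 23.2% | 26.4% | 3.2 | 1.14 | 0.37 |

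Example at q = 10%: control 1 − 0.90 × 0.96 = 0.136; rapid 1 − 0.90 × 0.92 = 0.172. In the control group, 0.10/0.136 = 74% of the counted events would have been present before treatment.

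**4. Yes/no outcome, unequal carry-over.** Same new-onset rates, so the true difference is +4.0 points.
- q = 20% in rapid teeth and 10% in control teeth: 26.4% − 13.6% = +12.8 points.
- q = 10% in rapid teeth and 20% in control teeth: 17.2% − 23.2% = −6.0 points.

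The text gives no rule for which tooth receives which material, so neither direction can be excluded.

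**5. Mean VAS.** Write the within-patient difference as D = δ + (B_rapid − B_control) + error, where B is carried-over pain. If B has the same mean for both materials, the expected value of D is δ: there is no dilution, only the added variance of B_rapid − B_control. Adjustment multiplies the SD by √(1 − r²), where r is the correlation between the within-patient pre-operative and post-operative differences. For assumed r of 0.3, 0.5 and 0.7 the factor is 0.95, 0.87 and 0.71.

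**The case against.** The strongest reply is that the plan already contains the problem. The score is used at entry, 3 is a ceiling, teeth with signs of pulpitis are excluded, and some restorations are replaced only because they are stained or unaesthetic. Many teeth may start at 0. All of this stands, and it limits the size. It does not remove teeth scored 1 to 3.

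A reader might infer more than the documents support:

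- *That carried-over pain is counted as post-operative.* This depends on a cut-off that the text does not give. A cut-off above 3 would remove much of it, and the restoration may itself relieve earlier sensitivity. Only *can be counted* is supported.
- *That carry-over always pulls the materials together.* Steps 4 and 5 show that this needs a yes/no outcome and equal persistence.
- *That the one-week baseline subtracts the treatment effect.* The plan defines the term openly, lists the pre-operative score separately, and plans no change-from-baseline analysis. The label could mislead an analyst, but nothing is subtracted as written.

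The illustration also has limits. The ratio falls steeply, but the absolute difference only from 4.0 to 3.2 points. Difference/SE is already 0.85 with no carry-over, so dilution is not what keeps 50 pairs from detecting 4% against 8%, and the plan specifies no test to which that ratio would apply. If the 4% is a total rate, q in the control group cannot exceed 4%, and under equal carry-over the difference then shrinks at most by the factor 0.96. At q = 20% both rates exceed the 0-20% range that the plan cites.

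Finally, the primary outcome also lacks a cut-off, a time point and a comparative test, so this is one part of a wider gap. It is still a separate part: fixing the others would not bring in the pre-operative score.

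**Conclusion.** The point holds in limited form. The pre-operative score is collected and then has no role beyond eligibility, so the primary outcome as planned cannot distinguish new from pre-existing sensitivity. This follows from the text and needs no assumption.

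The size is unknown because the documents give no distribution of pre-operative scores. Under a yes/no outcome with equal persistence, the difference shrinks by (1 − q): from 4.0 to 3.6 points at q = 10% and to 3.2 at q = 20%, with q and the 8% assumed and the 4% read as new onset. A mean VAS comparison would lose only precision. With unequal prior sensitivity the bias has no fixed sign. The plan should be changed because the remedy is nearly free and a pre-operative reading not taken cannot be recovered once the tooth is restored.

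**What to change.** 1. In Statistical Consideration, compare the two materials within patient on post-operative VAS, adjusted for each tooth's own pre-operative VAS. One simple form regresses the within-patient difference in post-operative VAS on the within-patient difference in pre-operative VAS; the intercept is the adjusted material difference.
2. Also report, by material, the share of teeth with new or increased sensitivity over the pre-operative score on the same stimulus.
3. Keep the raw post-operative distribution alongside.
4. State that the screening value, not the one-week visit called baseline, is the reference for sensitivity.
5. State that the screening assessment uses the same items as the Evaluation section (everyday triggers, air, biting, cold spray), where it does not already.

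The cost is a few extra minutes at a visit that already records pre-operative sensitivity, plus wording. One drawback is that an increase-based definition can miss new pain that replaces resolved caries pain, which is why item 3 stays.
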